### New Lesions

New lesions should be assessed and measured as they appear using RECIST 1.1 criteria (maximum of 5 lesions, no more than 2 per site, at least 10 mm in long axis (or 15 mm in short axis for nodal lesions), and recorded as New Lesions-Target (NLT) and New Lesion-Non-Target (NLNT) to allow clear differentiation from baseline target and non-target lesions.

New lesions may meet the criteria of NLT or NLNT to drive iUPD (or iCPD). However, the measurements of target lesions should NOT be included in the sum of measures of original target lesions identified at baseline. Rather, these measurements will be collected on a separate table in the case record form. These data will enable the development and testing of alternate response criteria, or further modifications of RECIST.

PD is confirmed in the New Lesion category if the next imaging assessment, conducted at least 4 weeks (but not more than 8 weeks) after iUPD confirms further progression from iUPD with either an increase of at least 5 mm in the absolute value of the sum of NLT OR an increase (but not necessarily unequivocal increase) in the size of NLNT lesions OR the appearance of additional new lesions.

### Time-point (TP) iResponse

Target Lesions*	Non-Target Lesions*	New Lesions*	Time Point Response	
			No prior iUPD**	Prior iUPD**
CR / iCR	CR	No	CR	iCR
CR/iCR	Non-CR/Non-PD Non-iCR/Non-iUPD	No	PR	iPR
PR/iPR	Non-CR/Non-PD Non-iCR/Non-iUPD	No	PR	iPR
SD/iSD	Non-CR/Non-PD Non-iCR/Non-iUPD	No	SD	iSD
iUPD with no change OR decrease from last TP	iUPD with no change OR decrease from last TP	Yes	NA	The appearance NLs confirms PD if Additional NLs or iUPD in last TP based on NLs and increase in size ( $\geq 5$ mm for NLT or any increase for NLNT) If no change in NLs from last TP, remains iUPD
PD	Non-CR/Non-PD Non-iCR/Non-iUPD	No	iUPD	Remains iUPD unless iCPD confirmed based on further increase in sum of at least 5 mm, otherwise remains iUPD

PD	PD	No	iUPD	iCPD if further increase in previously identified*** T lesion iUPD $\geq$ 5 mm and / or NT lesion iUPD
PD	PD	Yes	iUPD	iCPD if further increase in previously identified T lesion iUPD $\geq$ 5 mm and / or NT lesion iUPD and / or size or number of new lesion
Non-iUPD	Non-iUPD	Yes	iUPD	iCPD if increase in size of previously identified new lesions or increased number of new lesion

\* Using RECIST 1.1 principles. If no pseudoprogression occurs, RECIST 1.1 and iRECIST categories for CR, PR and SD would be the same.  
 \*\* In any category.  
 \*\*\* Previously identified in assessment immediately prior to this time-point (TP)  
 NA = not applicable.

### iRECIST Best Overall Response (iBOR)

All patients will have their iBOR from the start of study treatment until the end of treatment classified as outlined below.

TPR1	TPR2	TPR3	TPR4	TPR5	iBOR
CR	CR, PR, iUPD, NE	CR/iCR, PR/iPR, iUPD, iCPD, NE	iUPD	iCPD	iCR
iUPD	PR, SD, NE	CR	CR, PR, SD, iUPD, NE	CR, PR, SD, iUPD, iCPD, NE	iCR
iUPD	PR	PR, SD, iUPD, NE	PR, SD, iUPD, NE, cPD	PR, SD, iUPD, NE, iCPD	iPR
iUPD	SD, NE	PR	PR, SD, iUPD, NE	PR, SD, iUPD, iCPD, NE	iPR
iUPD	SD	SD, iUPD, NE	SD, iUPD, iCPD, NE	SD, iUPD, iCPD, NE	iSD
iUPD	iUPD	Anything	Anything	Anything	iCPD
iUPD	iUPD	iCPD	Anything	Anything	iCPD
iUPD	NE	NE	NE	NE	iUPD

1. Table assumes a randomized study where confirmation of CR or PR is not required.
2. NE = not evaluable that cycle.
3. Designation "I" for BOR can be used to indicate prior uPD to aid in data interpretation.
4. For patients with non-target disease only at baseline, only CR or non-CR/non-PD can be assigned at each TPR but is not shown in the table for ease of presentation.

### Methods of Measurement

The same method of assessment and the same technique should be used to characterize each identified and reported lesion at baseline and during follow-up. Assessments should be identified on a calendar schedule and should not be affected by delays in therapy, which may be treatment arm dependent. While on study, all lesions recorded at baseline should have their actual measurements recorded at each subsequent evaluation, even when very small (e.g. 2 mm). If it is the opinion of the radiologist that the lesion has likely disappeared, the measurement should be

recorded as 0 mm. If the lesion is believed to be present and is faintly seen but too small to measure, a default value of 5 mm should be assigned. For lesions which fragment/split add together the longest diameters of the fragmented portions; for lesions which coalesce, measure the maximal longest diameter for the “merged lesion”.

#### *Clinical Lesions*

Clinical lesions will only be considered measurable when they are superficial and  $\geq 10$  mm as assessed using calipers (e.g. skin nodules). For the case of skin lesions, documentation by colour photography including a ruler to estimate the size of the lesion is recommended. If feasible, imaging is preferred.

#### *Chest X-ray.*

Chest CT is preferred over chest X-ray, particularly when progression is an important endpoint, since CT is more sensitive than X-ray, particularly in identifying new lesions. However, lesions  $\geq 20$  mm on chest X-ray may be considered measurable if they are clearly defined and surrounded by aerated lung.

#### *CT, MRI.*

CT is the best currently available and reproducible method to measure lesions selected for response assessment. This guideline has defined measurability of lesions on CT scan based on the assumption that CT slice thickness is 5 mm or less. When CT scans have slice thickness greater than 5 mm, the minimum size for a measurable lesion should be twice the slice thickness. MRI is also acceptable in certain situations (e.g. for body scans). Other specialized imaging or other techniques may also be appropriate for individual case [82]. For example, while PET scans are not considered adequate to measure lesions, PET-CT scans may be used providing that the measures are obtained from the CT scan and the CT scan is of identical diagnostic quality to a diagnostic CT (with IV and oral contrast).

#### *Bone Scan.*

$^{99m}\text{Tc}$ -methylene diphosphonate radionuclide bone scintigraphy is the standard for bone imaging.

#### *Ultrasound.*

Ultrasound is not useful in assessment of lesion size and should not be used as a method of measurement. If new lesions are identified by ultrasound in the course of the study, confirmation by CT is advised.

#### *Endoscopy, Laparoscopy.*

The utilization of these techniques for objective tumor evaluation is not advised. However, they can be useful to confirm complete pathological response when biopsies are obtained or to determine relapse in trials where recurrence following complete response or surgical resection is an endpoint.

#### *Tumor Markers.*

Tumor markers alone cannot be used to assess objective tumor response. If markers are initially above the upper normal limit, however, they must normalize for a patient to be considered in complete response.

*Cytology, Histology.*

These techniques can be used to differentiate between PR and CR in rare cases if required by protocol (for example, residual lesions in tumor types such as germ cell tumors, where known residual benign tumors can remain). When effusions are known to be a potential adverse effect of treatment (e.g. with certain taxane compounds or angiogenesis inhibitors), the cytological confirmation of the neoplastic origin of any effusion that appears or worsens during treatment when the measurable tumor has met criteria for response or stable disease is advised to differentiate between response or stable disease and progressive disease.

### **11.3 Response and Stable Disease Duration (RECIST 1.1 and iRECIST)**

Response duration will be measured from the time measurement criteria for CR/PR or iCR/iPR (whichever is first recorded) are first met until the first date that recurrent or progressive disease is objectively documented, taking as reference the smallest measurements recorded on study (including baseline).

Stable disease duration will be measured from the time of registration/randomization until the criteria for progression are met, taking as reference the smallest sum on study (including baseline).

## **12. STUDY OVERSIGHT AND DATA REPORTING / REGULATORY REQUIREMENTS**

Adverse event lists, guidelines, and instructions for AE reporting can be found in [Section 7.0](#) (Adverse Events: List and Reporting Requirements).

### **12.1 Study Oversight**

The clinical research team will meet on a weekly basis when patients are being actively treated on the trial to discuss each patient. Decisions about dose level enrollment and dose modification if applicable will be made based on the toxicity data from prior patients.

All data will be collected in a timely manner and reviewed by the principal investigator or a lead associate investigator. Adverse events will be reported as required above. Any safety concerns, new information that might affect either the ethical and or scientific conduct of the trial, or protocol deviations will be immediately reported to the IRB using PROTECT and to the Sponsor. For adverse events related to either agent that have not been reported previously, voluntary MedWatch reporting will be performed.

The principal investigator will review adverse event and response data on each patient to ensure safety and data accuracy. The principal investigator will personally conduct or supervise the investigation and provide appropriate delegation of responsibilities to other members of the research staff.

## 12.2 Data Reporting

### Data Reporting

Medidata Rave is a clinical data management system being used for data collection for this trial/study. Access to the trial in Rave is controlled through the CTEP-IAM system and role assignments.

Requirements to access Rave via iMedidata:

- A valid account, and
- Assigned a Rave role on the LPO or PO roster at the enrolling site of: Rave CRA, Rave Read Only, Rave CRA (LabAdmin), Rave SLA, or Rave Investigator.

Rave role requirements:

- Rave CRA or Rave CRA (Lab Admin) role, must have a minimum of an Associate Plus (AP) registration type,
- Rave Investigator role, must be registered as an Non-Physician Investigator (NPIVR) or Investigator (IVR), and
- Rave Read Only role, site staff must have at a minimum an Associates (A) registration type.

- Refer to <https://ctep.cancer.gov/investigatorResources/default.htm> for registration types and documentation required.

Upon initial site registration approval for the study in Regulatory Support System (RSS), all persons with Rave roles assigned on the appropriate roster will be sent a study invitation e-mail from iMedidata. To accept the invitation, site staff must log in to the Select Login (<https://login.imedidata.com/selectlogin>) using their CTEP-IAM username and password, and click on the *accept* link in the upper right-corner of the iMedidata page. Site staff will not be able to access the study in Rave until all required Medidata and study specific trainings are completed. Trainings will be in the form of electronic learnings (eLearnings) and can be accessed by clicking on the link in the upper right pane of the iMedidata screen. If an eLearning is required and has not yet been taken, the link to the eLearning will appear under the study name in iMedidata instead of the *Rave EDC* link; once the successful completion of the eLearning has been recorded, access to the study in Rave will be granted, and a *Rave EDC* link will display under the study name.

Site staff that have not previously activated their iMedidata/Rave account at the time of initial site registration approval for the study in RSS will receive a separate invitation from iMedidata to activate their account. Account activation instructions are located on the CTSU website in the Data Management section under the Rave resource materials (Medidata Account Activation and Study Invitation Acceptance). Additional information on iMedidata/Rave is available on the CTSU members' website in the Data Management > Rave section at [www.ctsu.org/RAVE/](http://www.ctsu.org/RAVE/) or by contacting the CTSU Help Desk at [name] or by e-mail at [[contact]](mailto:[contact]).

### Monitoring Method

This study will be monitored by the Clinical Trials Monitoring Service (CTMS). Data will be submitted to CTMS at least once every two weeks via Medidata Rave (or other modality if approved by CTEP). Information on CTMS reporting is available at <http://theradex.com/clinicalTechnologies/?National-Cancer-Institute-NCI-11>. On-site audits will be conducted three times annually (one annual site visit and two data audits). For CTMS monitored studies, after users have activated their accounts, please contact the Theradex Help Desk at [contact] or by email at [[contact]](mailto:[contact]) for additional support with Rave and completion of CRFs.

### Responsibility for Data Submission

It is the responsibility of the PI(s) at the site to ensure that all investigators understand the procedures for data submission for the protocol and that protocol-specified data are submitted accurately and in a timely manner to the CTMS via the electronic data capture system, Medidata Rave. Data are to be submitted via Medidata Rave to CTMS on a real-time basis, but no less than once every 2 weeks. The timeliness of data submissions and timeliness in resolving data queries will be tracked by CTMS. Metrics for timeliness will be followed and assessed on a quarterly basis. For the purpose of Institutional Performance Monitoring, data will be considered delinquent if it is greater than 4 weeks past due. Data from Medidata Rave and CTEP-AERS is reviewed by the CTMS on an ongoing basis as data is received. Queries will be issued by CTMS directly within Rave. The queries will appear on the Task Summary Tab within Rave for the CRA to resolve. Monthly web-based reports are posted for review by the Drug Monitors in the IDB, CTEP. Onsite audits will be conducted by the CTMS to ensure compliance with regulatory requirements, GCP, and NCI policies and procedures with the overarching goal of ensuring the integrity of data generated from NCI-sponsored clinical trials, as described in the ETCTN Program Guidelines, which may be found on the CTEP ([http://ctep.cancer.gov/protocolDevelopment/electronic\\_applications/adverse\\_events.htm](http://ctep.cancer.gov/protocolDevelopment/electronic_applications/adverse_events.htm)) and CTSU websites.

CTMS will utilize a core set of eCRFs that are Cancer Data Standards Registry and Repository (caDSR) compliant (<http://cbiit.nci.nih.gov/ncip/biomedical-informaticsresources/interoperability-and-semantics/metadata-and-models>). Customized eCRFs will be included when appropriate to meet unique study requirements. The PI is encouraged to review the eCRFs, working closely with CTMS to ensure prospectively that all required items are appropriately captured in the eCRFs prior to study activation. CTMS will prepare the eCRFs with built-in edit checks to the extent possible to promote data integrity.

### **12.3 Collaborative Agreements Language**

The agent(s) supplied by CTEP, DCTD, NCI used in this protocol is/are provided to the NCI under a Collaborative Agreement (CRADA, CTA, CSA) between the Pharmaceutical Company(ies) (hereinafter referred to as “Collaborator(s)”) and the NCI Division of Cancer Treatment and Diagnosis. Therefore, the following obligations/guidelines, in addition to the provisions in the “Intellectual Property Option to Collaborator” ([http://ctep.cancer.gov/industryCollaborations2/intellectual\\_property.htm](http://ctep.cancer.gov/industryCollaborations2/intellectual_property.htm)) contained within the

terms of award, apply to the use of the Agent(s) in this study:

1. Agent(s) may not be used for any purpose outside the scope of this protocol, nor can Agent(s) be transferred or licensed to any party not participating in the clinical study. Collaborator(s) data for Agent(s) are confidential and proprietary to Collaborator(s) and shall be maintained as such by the investigators. The protocol documents for studies utilizing Agents contain confidential information and should not be shared or distributed without the permission of the NCI. If a copy of this protocol is requested by a patient or patient's family member participating on the study, the individual should sign a confidentiality agreement. A suitable model agreement can be downloaded from: <http://ctep.cancer.gov>.
2. For a clinical protocol where there is an investigational Agent used in combination with (an)other Agent(s), each the subject of different Collaborative Agreements, the access to and use of data by each Collaborator shall be as follows (data pertaining to such combination use shall hereinafter be referred to as "Multi-Party Data"):
  - a. NCI will provide all Collaborators with prior written notice regarding the existence and nature of any agreements governing their collaboration with NCI, the design of the proposed combination protocol, and the existence of any obligations that would tend to restrict NCI's participation in the proposed combination protocol.
  - b. Each Collaborator shall agree to permit use of the Multi-Party Data from the clinical trial by any other Collaborator solely to the extent necessary to allow said other Collaborator to develop, obtain regulatory approval or commercialize its own Agent.
  - c. Any Collaborator having the right to use the Multi-Party Data from these trials must agree in writing prior to the commencement of the trials that it will use the Multi-Party Data solely for development, regulatory approval, and commercialization of its own Agent.
3. Clinical Trial Data and Results and Raw Data developed under a Collaborative Agreement will be made available to Collaborator(s), the NCI, and the FDA, as appropriate and unless additional disclosure is required by law or court order as described in the IP Option to Collaborator ([http://ctep.cancer.gov/industryCollaborations2/intellectual\\_property.htm](http://ctep.cancer.gov/industryCollaborations2/intellectual_property.htm)). Additionally, all Clinical Data and Results and Raw Data will be collected, used and disclosed consistent with all applicable federal statutes and regulations for the protection of human subjects, including, if applicable, the *Standards for Privacy of Individually Identifiable Health Information* set forth in 45 C.F.R. Part 164.
4. When a Collaborator wishes to initiate a data request, the request should first be sent to the NCI, who will then notify the appropriate investigators (Group Chair for Cooperative Group studies, or PI for other studies) of Collaborator's wish to contact them.
5. Any data provided to Collaborator(s) for Phase 3 studies must be in accordance with the guidelines and policies of the responsible Data Monitoring Committee (DMC), if there is a DMC for this clinical trial.

6. Any manuscripts reporting the results of this clinical trial must be provided to CTEP by the Group office for Cooperative Group studies or by the principal investigator for non-Cooperative Group studies for immediate delivery to Collaborator(s) for advisory review and comment prior to submission for publication. Collaborator(s) will have 30 days from the date of receipt for review. Collaborator shall have the right to request that publication be delayed for up to an additional 30 days to ensure that Collaborator's confidential and proprietary data, in addition to Collaborator(s)'s intellectual property rights, are protected. Copies of abstracts must be provided to CTEP for forwarding to Collaborator(s) for courtesy review as soon as possible and preferably at least three (3) days prior to submission, but in any case, prior to presentation at the meeting or publication in the proceedings. Press releases and other media presentations must also be forwarded to CTEP prior to release. Copies of any manuscript, abstract and/or press release/ media presentation should be sent to: [contact]

The Regulatory Affairs Branch will then distribute them to Collaborator(s). No publication, manuscript or other form of public disclosure shall contain any of Collaborator's confidential/ proprietary information.

## 12.4 Human Data Sharing Plan

### *What data will be shared?*

We will share human data generated in this research for future research as follows:

- x De-identified data in an NIH-funded or approved public repository
- x Identified data in BTRIS (automatic for activities in the NIH Clinical Center)
- x De-identified or identified data with approved outside collaborators under appropriate agreements

### *How and where will the data be shared?*

Data will be shared through:

- x An NIH-funded or approved public repository: clinicaltrials.gov
- x BTRIS (automatic for activities in the NIH Clinical Center)
- x Approved outside collaborators under appropriate individual agreements
- x Publication and/or public presentations

### *When will the data be shared?*

- x At the time of publication or shortly thereafter

## 13. STATISTICAL CONSIDERATIONS

### 13.1 Study Design/Endpoints

The primary objective of this trial is to determine the safety, toxicity profile, DLTs, and MTD of rhIL-15 administered subcutaneously for 8 consecutive days in combination with anti-CTLA-4 and anti-PD1 monoclonal antibodies, in patients with metastatic or treatment-refractory cancers which are not curable or do not have known measures or treatments that are associated with a

survival advantage.

The exploratory objectives include characterization of the biological effects of this treatment on the percentages and absolute numbers of circulating lymphocyte sets (NK and T-cells) and T-cell subsets. The potential antitumor activity of rhIL-15 will be assessed by the clinical response rate and time to progression, as well as by measurement of T-cell infiltration into the tumor and immunologic gene expression in the tumor and in the periphery. Pre- and post-treatment fine-needle biopsies and blood samples throughout the study will be collected and analyzed.

The first 4-6 patients enrolling in the study will be placed into lead-in doublets (2-3 patients on each) and will receive a combination of rhIL-15 and either nivolumab OR ipilimumab. After completion of the doublet phase, the trial will be halted and a safety analysis will be submitted to the IRB. Once toxicity is cleared in both doublets (i.e., at least 2 patients enrolled on each doublet remain free of DLTs for 6 weeks) and a safety analysis is reviewed and approved by the IRB, new patients will be enrolled directly onto the triple agent dose escalation phase.

*As of Amendment C (10/3/18), toxicity has been cleared in both lead-in doublets. 3 patients were enrolled on Doublet A (rhIL-15 + nivolumab) and 2 patients were enrolled on Doublet B (rhIL-15 + ipilimumab); none of the 5 patients experienced a DLT in the 6-week period. The IRB has approved enrollment onto the triplet cohort.*

The dose escalation phase, which has 3 planned dose levels, is based on the prior clinical experience with each of the 3 investigational agents with the intent to define the MTD for the combination treatment.

The MTD will be based on the assessment of DLTs, and will be defined as the dose level at which less than one-third of patients (0/3 or 0-1/6 patients) treated at that dose experience a DLT, with the next higher dose level demonstrating a one-third or greater number of patients ( $\geq 2/3$  or  $\geq 2/6$  patients) having DLT. A DLT is defined as an AE that is felt to be related (possibly, probably, or definitely) to administration of study drugs, and meets prespecified criteria. This will include any condition requiring long-term treatment with corticosteroids or permanent discontinuation of one of the agents. If a subject did not experience DLT and did not finish 1 cycle of treatment (42 days), he or she will not be evaluable for determination of the MTD and will be replaced in the dose level.

Using the defined dose escalation scheme, the probability of escalating to the next dose level, based on the true rate of DLT at the current dose, is given by the following table (each group will be considered independently of the other):

True Toxicity at a Given Dose	10%	20%	30%	40%	50%	60%
Probability of Escalating	.91	.71	.49	.31	.17	.08

Thus, if the true underlying proportion of DLTs is 50% at the current dose, there is a 17% chance of escalating to the next dose.

Following the dose escalation cohort and determination of the MTD, another 15 patients will be treated at the MTD on an expansion cohort, which will include mandatory biopsies. With 15

patients and a tumor biopsy QA criteria failure rate of 50% with respect to paired (pre- and post-dose) biopsies, we have an 85% likelihood of having at least 6 usable PD samples, and 95% likelihood of having at least 5 usable samples from the expansion cohort. With 6 PD sample pairs, there is 90% power to detect a treatment effect equivalent to 1.85 SD's (associated with the intra-patient baseline variability of the PD marker) with the paired 2-sample T-test, at the 1-sided .05 significance level, for a given PD variable of interest. PD variables may be log-transformed to achieve more nearly normal distributions.

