#### 5.1.2.2 Expansion Cohort

An expansion cohort of 15 patients will be treated at the MTD or the maximum administered dose. With 15 patients and a biopsy QA failure rate of 50% with respect to paired biopsies, there is an 85% likelihood of having at least 6 usable samples and a 95% likelihood of having at least 5 usable samples.

Dose levels cohorts	Expansion cohort
rhIL-15 (mcg/kg/day)	MTD
Nivolumab (mg)	240
Ipilimumab (mg/kg)	1
Number of patients	15

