### **13.3 Analysis of Exploratory Endpoints**

Exploratory evaluations will be performed, with results reported with appropriate caveats about the exploratory nature of the analysis, and without formal adjustment for multiple comparisons.

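### The paired t-test named in Section 13.1 has about 86% power for 6 pairs at 1.85 intra-patient SDs under independent errors and equal variance, not 90%; no other assumption is stated

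*Combined protocol and SAP*

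**What the plan says.** Section 13.1 (Study Design/Endpoints) follows the biopsy-yield calculation for the expansion cohort with the plan's only power statement: "With 6 PD sample pairs, there is 90% power to detect a treatment effect equivalent to 1.85 SD's". The SD is described as "associated with the intra-patient baseline variability of the PD marker". The analysis is to be done "with the paired 2-sample T-test, at the 1-sided .05 significance level", for any one PD variable of interest. The scale is left open: "PD variables may be log-transformed to achieve more nearly normal distributions".

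The plan gives no SD for the pre/post difference, no residual correlation between pre- and post-dose errors, and no ratio of post-dose to baseline variance.

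Section 5.1.2.2 (Expansion Cohort) supports the 15 patients by biopsy yield alone, including "a 95% likelihood of having at least 5 usable samples". Section 13.3 says exploratory evaluations will have their "results reported with appropriate caveats about the exploratory nature of the analysis", without multiplicity adjustment.

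**The concern.** The sentence measures the effect in one SD and names a test that depends on another. A paired t-test divides the mean change by the standard error of the within-patient differences. The SD cited is the variability of the marker within a patient at baseline. To get from one to the other, one must know how the pre- and post-dose errors are correlated and whether treatment changes the variance. Nothing is said on either.

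The usual default is independent errors with equal variance. Using an intra-patient SD already removes the between-patient component, so any further positive correlation would be an extra assumption. Under that default the claimed 90% does not follow.

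Little is at stake: whether a reader can reproduce the plan's single power claim, and apply it to a given marker. As written, the detectable effect for 6 pairs looks somewhat smaller than the named test supports.

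**Working it through.** **Inputs, all from Section 13.1:** n = 6 pairs; effect d = 1.85 in units of the intra-patient SD, σ; one-sided α = .05; paired t-test, so df = 6 − 1 = 5 and the critical value is t(.95, 5) = 2.015.

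**Formula.** Let k = SD(difference)/σ. The noncentrality parameter is d√n / k, and power is the probability that a noncentral t with 5 df exceeds 2.015. In general k² = 1 + v − 2ρ√v, where v is the post-dose to baseline variance ratio and ρ the residual correlation.

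**1. Trying to reproduce the 90%.** Three standard readings at d = 1.85:

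| Reading | Noncentrality | df | Power at 1.85 | Effect giving 90% |
|---|---|---|---|---|
| Paired, k = √2 (independent errors, equal variance) | 1.85 × √3 = 3.204 | 5 | 86.3% | 1.98 SD |
| Paired, SD taken as that of the differences (k = 1) | 1.85 × √6 = 4.532 | 5 | 98.6% | 1.40 SD |
| Unpaired two-sample, 6 per group | 1.85 × √3 = 3.204 | 10 | 90.9% | 1.82 SD |

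Only the unpaired test comes near 90%, and it is not the test named. It is shown for comparison; the documents do not reveal how the 90% was obtained. A simulation of 1,000,000 trials for the first row gave 86.3%.

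**2. The effect that does give 90%.** For 5 df, 90% power needs a mean change of 1.4010 SD of the difference. In intra-patient SDs with k = √2 this is 1.4010 × 1.4142 = 1.981, and 1.981 / 1.85 = 1.071, so about 7% larger than stated.

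**3. What would make the sentence true.** 90% at 1.85 requires k = 1.85 / 1.4010 = 1.3205, so k² = 1.744.

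- Equal variances: ρ = 1 − 1.744/2 = 0.128.
- Independent errors: v = 1.744 − 1 = 0.744.

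**4. Sensitivity, 6 pairs at 1.85 intra-patient SDs.**

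| Residual correlation (equal variance) | Power | Variance ratio (independent errors) | Power |
|---|---|---|---|
| −0.10 | 83.3% | 0.50 | 93.4% |
| 0 | 86.3% | 0.74 | 90.1% |
| 0.10 | 89.2% | 1.00 | 86.3% |
| 0.13 | 90.1% | 1.25 | 82.6% |
| 0.20 | 92.0% | 1.50 | 79.1% |

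**5. Other numbers of pairs (k = √2).** Seven pairs give 91.8%. Averaged over a Binomial(15, .5) yield, power is 90.1%; averaged over yields of 6 or more, it is 93.8%.

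**6. Biopsy yield.** With 15 patients and a 50% failure rate:

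- P(at least 6) = 1 − (1 + 15 + 105 + 455 + 1365 + 3003)/32768 = 1 − 4944/32768 = 0.849. The stated 85% is right.
- P(at least 5) = 1 − 1941/32768 = 0.941. The stated 95% should be 94%.

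**The case against.** The strongest reply is that no arithmetic slip has been proved. The 86% rests on independent errors and equal variance, and the plan asserts neither. A residual correlation of only about 0.13 restores 90%. This stands in part: the shortfall is conditional, and the documents do not show whether it comes from an unstated assumption or a miscalculation. But the plan supplies no condition that yields 90%, and modest departures the other way lower power further.

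A second reply is that the link between the SD and intra-patient variability is loosely worded, and the SD of the differences may have been meant. Power would then be 98.6% and the plan would be understating it. So the direction of the discrepancy does depend on which SD is meant. The literal wording points to baseline variability rather than to change, however, and 98.6% does not reproduce 90% either.

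Third, under the same default assumptions, power averaged over the expected biopsy yield is 90.1%, close to what the plan claims. That is fair comment on the cohort as a whole, but the sentence makes its claim for exactly 6 pairs.

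It can also be said that effects in SD units may serve either a raw or a log scale. That is reasonable, and the scale is a secondary point. The 95% against 94% is a separate rounding matter and adds nothing to the power argument.

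**Conclusion.** The point holds, as a minor one. With the SD that Section 13.1 names, independent errors and equal variance, 6 pairs give 86.3% power at 1.85 SD. This is 3.7 points below the stated 90%, and 90% needs 1.98 SD. The other natural reading of the paired test misses 90% in the opposite direction.

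Nothing in the design depends on the figure. The PD analyses are exploratory and reported with caveats, the 15 patients are justified by biopsy yield, and neither the 90% nor the 1.85 enters a sample size, stopping rule, or DLT or MTD decision.

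**What to change.** Replace the power sentence in Section 13.1 with, for example:

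> For 6 evaluable biopsy pairs, a paired t-test on the within-patient differences (5 df, one-sided α = .05) has 90% power for a mean change of 1.40 SD of the paired difference. This equals 1.98 intra-patient SDs if pre- and post-dose errors are independent with equal variance; under the same assumptions, power at 1.85 intra-patient SDs is 86%.

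If the sponsor has grounds for keeping 1.85 with 90%, the sentence should instead state the correlation or variance assumption that makes the SD of the difference 1.32 times the intra-patient SD, its source, and whether the SD is on the raw or log scale.

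Editorially, change 95% to 94% for at least 5 usable pairs in Sections 13.1 and 5.1.2.2.

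The cost is one sentence and one digit in two places. Sample size, analysis and conduct do not change.
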